
2. Study objectives or hypotheses

a. Hypotheses:

Homozygous carriers of the 118A allele of the μ -opioid receptor will show greater positive subjective response to the morphine than those carrying one or two copies of the

118G allele (118GX), paralleled by lower binding potential for [¹¹C] raclopride following morphine injection because of greater dopamine release than carriers of the G allele.

Objectives:

- a. Primary objectives:** To examine the role of the μ -opioid receptor polymorphism OPRM1 A118G on the subjective and objective effects, including dopamine release, of the μ -opioid agonist morphine.
- b. Secondary objectives:** A number of exploratory analyses will be carried out with the collected data to generate hypotheses on the relation of patient characteristics (e.g. family history of alcohol/drug use disorders, pain, mood, etc.), physiological opiate responses (e.g., pupil constriction, cardiovascular parameters such as respiratory rate and % oxygen saturation as measured by Pulse Ox), endocrine responses (cortisol, ACTH), pain threshold (measured by cold pressor test), MRI scans, and positive psychological effects (as measured via visual analog scale) with DA release measured by PET.

3. Subjects

a. Description of study populations

i. Brief description of subject groups

Subjects will be 21-55 year-old, non-nicotine dependent male volunteers who have taken prescription pain pills without negative effects in the past, but are not currently taking them or dependent on them. All participants will be in good health, non-smokers or light smokers (< 20 cigarettes/week), current non drinkers or social drinkers; participants should not meet DSM IV criteria for alcohol abuse or alcohol dependence. Subjects will be recruited into two groups: 1) subjects homozygous for the major 118A allele (118AA genotype) of the OPRM1 polymorphism; 2) subjects carrying one or two copies of the variant 118G allele (118AG or 118GG genotype, hereafter called 118GX) of the OPRM1 polymorphism.

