Post-placebo) and post-morphine injection measures will be made in two areas: 1) subjective response as measured by a standardized questionnaire (DEQ), and 2) objective measures response. We will determine their response to a cold pressor pain test, and a measurement of their pupillary constriction as well as several other tests of their response to the morphine, including continuous Pulse Ox monitoring and intermittent monitoring of their respiratory rate, heart rate, EKG and blood pressure. Blood will be collected to measure plasma ACTH and cortisol levels as they may be suppressed by activation of the μ -opioid receptor. Retrospectively, participants will be asked to evaluate their peak experience to the morphine on a Likert-like visual analog scale (VAS), which will include sedation, euphoria, dizziness, fatigue, depression, tremors, anxiousness, upset stomach/nausea, dry mouth, and headache, which are common side effects of opiate administration (Appendix I). We hypothesize that 118AA subjects will have significantly higher subjective response to the morphine challenge than 118GX subjects.

On two more separate visits, at least a week apart (Visits 3 and 4), participants will report to the Clinical Center in Bethesda for an overnight stay before each PET scan. We will repeat the injection procedure in all participants twice in the PET scanner, once injecting morphine and once injecting saline, and assess the binding potential of [¹¹C]raclopride, a positron emitter labeled ligand which binds preferentially to D2 dopamine receptors. The difference between the binding potential following the saline injection and that during the morphine injection will provide a measure of dopamine release. We hypothesize that 118AA subjects will have a lower binding potential with [¹¹C]raclopride from the morphine injection relative to placebo, indicating greater amounts of dopamine release than those subjects carrying one or two copies of the G allele.

b. Recruitment

This study employs an experiment of nature, i.e. genetic variability, as a basis for group assignment. To obtain the respective groups, this protocol will be conducted in the following phases:

1. Recruitment of potential participants through approved advertising media (see draft ad in Appendix II).
2. Thorough screening of selected participants according to 06-DA-N415 (“Screening Protocol for the Evaluation of Potential Research Subjects”).

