At 5 min following the morphine, which will be administered by an NIH Credentialled physician with ACLS certification, or placebo injection, up to 12 mCi [¹¹C]raclopride will be administered as a bolus over one minute into the IV line in the opposite arm. Monitoring of HR, RR, BP, EKG and oxygen saturation will begin immediately by an NIH Credentialled physician. Values will be recorded every 5 min for the duration of the PET scan by the nurse or nurse practitioner monitoring the study. The participant will be asked how he feels in addition to the administration of the DEQ in the event he feels nauseous or needs to vomit. He will also be encouraged to tell the study staff at any time if he feels nauseous or needs to vomit. In the event that the participant experiences either of these side effects, he will be removed from the scanner until the effects subside or if they do not, the study will be discontinued. As the participant cannot easily view the DEQ in paper form or on a computer while he is in the scanner, he will be asked to provide a number between 0 and 100 in response to the four DEQ questions. An NIH Credentialled physician with ACLS certification, will continue to monitor these values for 60 min or until the values return to normal ranges. Dynamic PET scans will begin with the [¹¹C]raclopride injection and continue approximately 90 minutes to obtain optimal signal.

The PET data from the placebo day will be used as a measure of baseline raclopride binding potential, using the Simplified Reference Tissue Model outlined by Lammertsma and Hume (1996). PET measurements taken following the morphine injection will be compared to that derived from placebo injection to measure the reduction in specific binding due to competition with dopamine endogenously released by the morphine challenge. The percent change from baseline has been shown to be proportional to the magnitude of dopamine release (Watabe et al. 2000).

Table for Visits 3 and 4

Minutes	BL	0	5	10	15	20	25	30	35	40	45	50	55	60	70	80	90	95
Morphine or placebo administration		x																
[¹¹ C]Raclopride injection, start scanning			x															
HR, BP, RR, O ₂ Sat, EKG recorded*	x		x	x	x	x	x	x	x	x	x	x	x	x	x	x	x	x
DEQ	x			x		x		x		x		x		x				
End scanning																	x	
VAS																	x	

Please note timing for these parameters will be as close as possible to the stated times, but may not be at exactly these times.

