To evaluate for the possibility of adverse events, a safety assessment evaluation will be conducted at the completion of the last of the PET scan / injection study sessions. This assessment will include vital sign determination, EKG, CBC, and blood chemistry. The Lead Investigator or her designate will contact the participant by phone, approximately one week after the completion of the study to evaluate for the possibility of any unexpected adverse events.

Participants will be withdrawn from the study if they do not follow the instructions outlined in the protocol and informed consent form. Participants will also be withdrawn if they cannot tolerate the morphine injection and demonstrate any signs of untoward effects. Participants may also, at any time, choose to discontinue their participation in the study.

9. Outcome measures

- a. The two primary outcome measures are:
 - 1) $[^{11}\text{C}]\text{raclopride}$ binding potential in striatal areas of the brain
 - 2) Subjective perceptions of morphine intoxication and opiate effects.
- b. Secondary measures are:

- 1) levels of neuroendocrine measures (ACTH, cortisol)
- 2) pupillary constriction, respiratory rate, pain response

10. Statistical Analysis

a. Analysis of data/ study outcomes

For the primary analyses, dependent variables (subjective and objective responses in the laboratory, post-morphine injection raclopride binding potential) will be analyzed using analysis of variance, with genotype as the independent factor. The role of drug and alcohol drinking history and family history of drug abuse/alcoholism as well as self-reports of ancestry and genetically derived ancestry scores will be evaluated as covariates in the analysis. The level of significance will be set at 0.05.

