PET Analysis will be based on a Region of Interest (ROI) methodology. MRI scans will be performed on each participant, and co-registered with the participant's PET scans. ROIs will be drawn in the nucleus accumbens, dorsal and ventral caudate and putamen, these being the main areas of post-synaptic dopamine release. An ROI will also be placed on the cerebellum as this region is thought to be devoid of dopamine receptors and is used as the reference region because it provides a measure of nonspecific binding (Lammertsma and Hume 1996). Dopamine release will be estimated by comparing [¹¹C]raclopride binding potential derived using a bolus injection and the simplified reference tissue model (SRTM) under two different conditions (baseline vs. morphine) during separate scans conducted in randomized order.

Baseline binding potential, changes in binding potential following morphine challenge, and subjective effects of the challenge as measured by changes in stimulation and intoxication scores on subjective perception scales between dose conditions (opiate vs. placebo) will be correlated.

a. Power analysis

Sample size:

In a study that evaluated the effect of remifentanil administration on D2 dopamine receptor availability using a different PET radioligand in detoxified alcohol dependent participants (N=11) and controls (N=11) found a significantly reduced dopamine D2/3 receptor availability after administration compared with baseline in the ventral striatum (9.5%) and the dorsal putamen (8.3%) in both groups (Spreckelmeyer et al. 2011). We can expect similar reductions due to DA release after morphine in one or both research groups (118A homozygotes; 118GX). A study that evaluated the effect of the variants of the OPRM1 genotype in social drinkers compared during placebo and alcohol infusions found a significantly greater DA release as measured by Δ binding potential in those participants who carried the G allele (N=12) compared to the 118 homozygotes (N=16) (Ramchandani et al. 2011). However, results of the studies in the humanized mouse strains of these two genotypes yielded opposite effects of genotype on DA release from morphine.

If the results of this study yield similar results, 40 completers per group should provide adequate power to detect effects of OPRM1 genotype. We estimate that to have this number of completers, we must screen and genotype at least 120 prospective participants.

[figure not shown]

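### The correlation list in section 10a does not exclude baseline binding potential against a change computed from the same placebo scan; that pair should not be tested against zero

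*Combined protocol and SAP*

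**What the plan says.** The last paragraph of section 10a (Analysis of data/study outcomes) names three quantities: "Baseline binding potential, changes in binding potential following morphine challenge, and subjective effects of the challenge". The last of these is measured by changes in scores on perception "scales between dose conditions (opiate vs. placebo) will be correlated". The sentence names no pairs, coefficient, null value or p-value, and it leaves no pair out.

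The definitions come from three places:

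- **Baseline.** Section 4d (Detailed description of PET procedure): "The PET data from the placebo day will be used as a measure of baseline raclopride binding potential".
- **Change.** Section 4a (Study overview) takes "The difference between the binding potential following the saline injection and that during the morphine injection" as the measure of dopamine release. Section 4d also refers to a percent form: "The percent change from baseline has been shown to be proportional to the magnitude of dopamine release".
- **Scans.** Section 10a compares BP "under two different conditions (baseline vs. morphine) during separate scans conducted in randomized order". Each man has two PET sessions, one saline and one morphine, so there is no third scan that could serve as an independent baseline.

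The only significance level, "The level of significance will be set at 0.05", closes the paragraph on the primary genotype analyses. The secondary objectives in section 2 describe exploratory analyses relating patient characteristics, physiological and endocrine responses, pain threshold, MRI scans and "positive psychological effects (as measured via visual analog scale) with DA release measured by PET". They do not name baseline BP as a correlate of release.

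**The concern.** If a measured baseline X is correlated with a change built from X, chance error in X enters both variables. A placebo scan that happens to read high raises the baseline and also raises the apparent release. BP can also be tied to the change by scale. If release is a fixed fraction of BP, absolute change is larger in men with higher BP. If release is a fixed amount, percent change is smaller in men with higher BP. Zero is then not the value expected when release and true baseline are unrelated.

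What is at stake is one interpretation. A significant baseline-change correlation could be reported as evidence that baseline D2 receptor availability predicts morphine-induced dopamine release, when it reflects how the two numbers are constructed. Section 10a defines several striatal ROIs, so the same pair could recur in each.

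**Working it through.** **The plan's own figure.** The plan gives no figure for these correlations. Its only power calculation is for the genotype ANOVA: f = 0.65, alpha 0.05, power 0.80, total N = 22. It reproduces: lambda = 22 × 0.65² = 9.295, critical F = 4.3512 on (1, 20) df, power 0.826. Only f = 0.65 is carried forward here.

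**Inputs from the documents.** 80 completers (40 per genotype); level 0.05 (sidedness not stated, taken as two-sided); f = 0.65; reductions in receptor availability of 8.3% and 9.5% in the cited remifentanil study, which suggest a mean release near 9%.

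**Inputs assumed, because the documents do not give them.** Between-subject CV of BP 12%; release SD 5% of mean BP; test-retest reliability r = 0.95, 0.90 or 0.80; release independent of true baseline.

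**Model.** Mean BP is scaled to 1. Placebo scan X = T + e1. Morphine scan Y = T − d + e2 (additive release) or T(1 − d) + e2 (proportional release). Change is X − Y (absolute) or (X − Y)/X (percent). Coding change as morphine minus saline reverses the signs.

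**Closed form: absolute change with additive release only.** Write V for the variance of X. Then Cov(X, X − Y) = Var(e1) = (1 − r)V and Var(X − Y) = 2(1 − r)V + SD_release². Hence

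corr = (1 − r) / sqrt(2(1 − r) + (SD_release/SD_BP)²).

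With SD_release/SD_BP = 0.05/0.12, whose square is 0.174:

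- r = 0.95: 0.05/sqrt(0.274) = 0.096
- r = 0.90: 0.10/sqrt(0.374) = 0.164
- r = 0.80: 0.20/sqrt(0.574) = 0.264

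A genotype difference of f = 0.65 adds variance to change but not to X, so each value is divided by sqrt(1 + 0.65²) = 1.193. This gives 0.080, 0.137 and 0.221. The critical |r| at N = 80 is 0.220.

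**Absolute change with proportional release.** The covariance gains a term: Cov = (1 − r)V + (mean release) × rV. At r = 0.90 this is 0.10V + 0.09 × 0.90V = 0.181V instead of 0.10V. The closed form above does not apply, and part of the correlation is scaling rather than scan error.

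**Rejection rates of a nominal 5% Pearson test against zero** (simulation, 20,000 runs per cell, N = 80, f = 0.65, release SD 5%):

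| Change | Release | r = 0.95 | r = 0.90 | r = 0.80 |
|---|---|---|---|---|
| Absolute | Additive | 11% | 23% | 51% |
| Absolute | Proportional | 49% | 60% | 78% |
| Percent | Proportional | 11% | 22% | 47% |
| Percent | Additive | 10% | 6% | 21% |

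In the last row the mean correlation changes sign: −0.07, +0.02, +0.13.

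**Separating the two sources.** With no scan error (r = 1), release SD 5% and no genotype difference, rejection is about 5% for absolute/additive and percent/proportional, so scan error accounts for the excess there. It is about 47% for absolute/proportional and 49% for percent/additive (correlation −0.21), where scaling alone links the two.

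**Sensitivity.** With release SD 10% and f = 0.65, rejection is 7/12/29% (absolute/additive), 7/12/28% (percent/proportional) and 7/6/14% (percent/additive). With CV 8% or 16%, the absolute/additive row becomes 8/16/39% or 13/27/57%.

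**The other two pairs.** Baseline or change against an unrelated subjective score rejects 4.8–5.2%, so those correlations are sound.

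**The case against.** The strongest reply is that the plan does not write this analysis down. The sentence can be read as relating each PET measure to subjective effects, the only item it goes on to define in detail. The 0.05 level belongs to the primary-analysis paragraph, and the secondary objectives do not list baseline BP as a correlate of release. Harm needs three unstated steps: the pair is run, it is tested against zero, and the result is read as biology. All of this stands. A reader might infer that the plan commits to testing baseline against change at 0.05; the documents do not say so. What remains is that the sentence does not exclude the pair, and the two PET measures stand side by side in the list.

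A second reply is that the size is unknown. That also stands. Reliability, CV and release SD are all assumed, and for percent change, the form that section 4d ties to dopamine release, some cells are near nominal. A reader might equally take one of the high rates as the expected error or as a ceiling. Neither is supported. With identical release in every man, absolute change rejects 29/52/83% under additive release but about 96–98% under proportional release, so no upper bound is claimed.

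A third reply is that this is a general caution for any baseline-and-change study. It is, but here the shared scan is documented and no independent baseline is planned.

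**Conclusion.** The concern holds in a limited form. Section 10a, read plainly, includes a pair whose two members share the placebo scan, and zero is generally the wrong reference value for it. The excess over 5% comes from shared scan error and, depending on how change is expressed and how release behaves, from scaling with BP. Under the stated assumptions rejection runs from about 6% to 78%. Where in that range the trial would fall cannot be settled from the documents, because they fix neither the reliability, CV and release SD nor one form of change.

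A reader might infer that the dopamine-release findings as a whole are biased. The documents do not support that. The genotype ANOVAs and the sample size do not use this correlation, and subjective effects share no scan with either BP measure. The exploratory label is itself inferred from the secondary objectives, since section 10a does not attach it to these correlations. This is a minor point that the sponsor could usefully settle in the wording.

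**What to change.** In the last paragraph of section 10a, state that baseline BP and change in BP will each be correlated with subjective effects, and that baseline BP against change in BP will not be tested against zero in any ROI. If the baseline-change relation is shown, label it descriptive and note that both quantities use the placebo scan.

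The cost is a short change to the analysis text. It needs no new data and no change to the sample size or conduct. What is given up is one exploratory p-value per ROI.

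### Section 10 correlates binding-potential change with subjective effects without a genotype term, so genotype differences on both measures would produce a correlation even with no relation within genotype

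*Combined protocol and SAP*

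**What the plan says.** Section 10 (Analysis of data/study outcomes) plans to relate three quantities: baseline binding potential, its change after morphine, and the subjective effects of the challenge. It says that these, with the last measured as score changes "on subjective perception scales between dose conditions (opiate vs. placebo) will be correlated". It names no coefficient, stratum, adjustment or partial correlation.

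In Section 10 genotype enters only through the primary analysis, where the dependent variables "will be analyzed using analysis of variance, with genotype as the independent factor". The covariates attached to that analysis are drug and drinking history, family history and ancestry ("self-reports of ancestry and genetically derived ancestry scores will be evaluated as covariates in the analysis"). Genotype is not in that list, and the correlation sentence does not refer to it.

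Section 2 (Hypotheses) expects the groups to differ on both correlated variables. Men homozygous for the A allele "will show greater positive subjective response to the morphine than those carrying one or two copies of the" G allele, together with lower binding potential "because of greater dopamine release than carriers of the G allele". Section 2 (Secondary objectives) adds associations of patient characteristics, physiological, endocrine, pain and MRI measures, and positive psychological effects "with DA release measured by PET", under the statement "A number of exploratory analyses will be carried out with the collected data to generate hypotheses".

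Inclusion criterion 5 (Section 3) and the power analysis (Section 10) fix the sample at 40 completers per genotype.

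**The concern.** Across a sample built from two groups, an unadjusted correlation mixes two things: how the variables move together among men of the same genotype, and how far apart the group means lie. Only the first bears on whether men who release more dopamine feel more drug effect, over and above what genotype does to each measure. The second arises whenever genotype shifts both variables, by whatever route.

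This trial is exposed because the groups are selected by genotype, are forced to equal size, and are expected to differ on both variables. At stake is the reading of a secondary result. A significant correlation could be reported as a brain-behaviour link when it only restates the two genotype differences. If genotype shifts the variables in opposite directions, a real relation could be missed. The protocol summary states the subjective hypothesis only as a difference, without direction, so opposite shifts cannot be ruled out.

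**Working it through.** **Inputs from the plan.** 40 men per genotype, N = 80. The significance level comes from "The level of significance will be set at 0.05" and is taken as two-sided. The genotype effect f = 0.65 comes from the power analysis in Section 10, which takes it from an earlier alcohol-challenge study. That section describes the study's genotype result as a difference in dopamine release. With two equal groups, d = 2f = 1.30.

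**Assumptions.** The genotype effect on subjective response is not given in the documents, so it is varied from f = 0 to 0.65. Change in binding potential is coded as a reduction, so that more release is a higher value. Both variables are normal with unit SD within genotype.

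**The plan's own figure.** λ = N·f² = 22 × 0.65² = 9.295. The critical F on (1, 20) degrees of freedom is 4.3512 and power is 0.8263. This reproduces the stated total of 22. The plan gives no figure for the correlation analysis.

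**Correlation produced by group means alone.** With equal groups and zero correlation within genotype,

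r = f₁f₂ / √[(1 + f₁²)(1 + f₂²)].

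For f₁ = f₂ = 0.65, r = 0.4225 / 1.4225 = 0.297. For 0.65 and 0.25, r = 0.1625 / √(1.4225 × 1.0625) = 0.132. The two-sided 5% critical value of |r| for N = 80 is 0.22.

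**Rejection rates.** 40,000 simulated trials per row, 40 men per genotype, zero correlation within genotype:

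| f, dopamine release | f, subjective effect | Expected r | Unadjusted test significant | Genotype-adjusted test significant |
|---|---|---|---|---|
| 0.65 | 0 | 0 | 5% | 5% |
| 0.65 | 0.10 | 0.05 | 8% | 5% |
| 0.65 | 0.25 | 0.13 | 22% | 5% |
| 0.65 | 0.40 | 0.20 | 45% | 5% |
| 0.65 | 0.65 | 0.30 | 80% | 5% |
| 0.317 | 0.317 | 0.09 | 13% | 5% |
| 0.25 | 0.25 | 0.06 | 8% | 5% |

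f = 0.317 (d = 0.63) is the effect that 80 men detect with 80% power. The adjusted test is the partial correlation given genotype, with N − 3 = 77 degrees of freedom.

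**Masking.** Take a true within-genotype correlation of 0.4 and genotype shifts in opposite directions. At d = 1.0 (f = 0.5) on each variable, the expected unadjusted r is (0.4 − 0.25) / 1.25 = 0.12. The unadjusted test is significant in about 16% of trials and the adjusted test in about 96%. At opposite shifts of d = 1.3, the figures are about 3.5% and 96%.

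**The case against.** **The text is silent; it does not say that the groups will be pooled.** True. The single correlation over 80 men is a reading of an unspecified analysis. But taken at face value the sentence describes an unadjusted correlation, and nothing elsewhere in the plan supplies a genotype term.

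**Nothing important rests on it.** Largely right. The correlation is not a primary or secondary measure in Section 9, and Section 2 calls associations with dopamine release exploratory. A reader might infer that it is the plan's evidence that subjective response parallels dopamine release. The documents do not say so: the parallel in Section 2 is a statement about groups, and the genotype analyses of variance on the two outcomes address it directly.

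**The high rates need an effect size that the plan does not give.** This also stands. A reader might take f = 0.65 as the planned effect on both outcomes, but the protocol gives it from an alcohol study whose reported genotype difference was in dopamine release, and sizes the trial for somewhat smaller effects. If either genotype effect is zero, the unadjusted test keeps its 5% error rate.

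**The unadjusted correlation is legitimate.** If genotype acts on subjective response through dopamine, the between-genotype variation is part of the relation of interest. That is a reason to show the unadjusted correlation, but not to rest a claim on it alone, because it cannot separate this mechanism from two independent genotype effects.

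**Conclusion.** The point holds for the correlation as written. If genotype shifts both variables, the unadjusted correlation is non-zero without any relation within genotype. Adjusting for genotype brings the error rate back to about 5% in every scenario examined.

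The size depends on an effect that the documents do not state. With f = 0.65 for dopamine release, the false-positive rate runs from 5% to 80% as the subjective f goes from 0 to 0.65.

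Two stronger readings are not supported. One is that success on both primary outcomes would largely produce the correlation: at f = 0.317 on both, where each genotype test has 80% power, it is significant in only about 13% of trials. The other is that every association in the secondary objectives is affected. Section 2 hypothesises genotype differences for subjective response and dopamine release, and the artefact needs a shift in both members of a pair.

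The primary analysis of variance and the sample size do not depend on this point. The change is worth making because genotype is already recorded and the better analysis is nearly free.

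**What to change.** In Section 10 (Analysis of data/study outcomes), state that any claim that dopamine release tracks subjective effect will rest on a genotype-adjusted analysis: either the partial correlation given genotype, or a regression of subjective change on binding-potential change with a genotype term. Show the unadjusted correlation and the two group-specific slopes descriptively beside it. State whether change in binding potential is coded as a reduction or as a signed change, since this sets the sign of the correlation.

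Apply the same adjustment to those associations with dopamine release in the secondary objectives of Section 2 where genotype may shift both variables.

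The cost is a few sentences and one degree of freedom for the adjusted test. No new data are needed. Little real signal is lost: with a true within-genotype correlation of 0.4 and shifts of d = 1.3 in the same direction on both variables, the adjusted test keeps about 96% power.
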